30 to classical methods. In SIRIUS we will prospectively challenge this hypothesis to address the
31 question of how often a better or final diagnosis can be delivered by WGS and/or WTS and if
32 unclear cases can be efficiently resolved.

33

34 **Type of Research:** observational study, diagnostic study, hematology, leukemia, next
35 generation sequencing

36

37 **Intervention:** none

38 **APPROVAL**

39 This study will be conducted with the utmost respect for individual patients in accordance with
40 the requirements of this diagnostic trial protocol and especially in accordance with the
41 following:

42 • Good clinical practice directive (European Union) (2005/28/EC)

43 • The ethical principles in accordance with the Declaration of Helsinki

44 • International Conference on Harmonization (ICH) E6 Good Clinical Practice:
45 consolidated guideline

46 • Guidelines for Good Clinical Practice (*Deutsche Forschungsgemeinschaft DFG*)

47 • Standards and guidelines for the interpretation of sequence variants (PMID: 25741868)

48 • All applicable laws and regulations, including, without limitation, data privacy laws,
49 clinical trial disclosure laws, and regulations.

50 **I. INTRODUCTION**

51 1. Background and Rationale

52 Treatment of hematological diseases relies on a single cardinal prerequisite: correct
53 classification within the broad specter of malignant diseases arising from the hematopoietic
54 system. With the ever-expanding availability of distinct yet complementary diagnostic tools,
55 our understanding of the landscape of hematological diseases steadily increases. As such, the
56 current consensus classification as summarized through the WHO classification (2017)
57 represents a compass guiding diagnostic algorithms to the correct diagnosis. Today, the gold
58 standard of routine diagnostic process relies on five methodological pillars: cytomorphology,
59 histology, chromosomal cytogenetics, immunophenotyping, and molecular genetic testing.
60 This leads to a treatment enabling diagnosis in the vast majority of cases. However,
61 approximately 10 % of cases remain unresolved from a diagnostic point of view and hence do
62 not lead to a satisfactory diagnosis according to current WHO standards (2017). We intend to
63 solve this issue to provide illuminating diagnostic guidance for the best possible patient's care.

64 2. Objectives

65 To address this problem, we hypothesize that novel high throughput sequencing methods, e.g.,
66 whole genome and/or whole transcriptome sequencing are able – by virtue of painting a more
67 delicate genetic portrait of a tumor sample – to provide a more accurate diagnosis.
68 To this end we generated a reference collection of 5,500 samples with the full spectrum of
69 hematological malignancies, for which we performed whole-genome sequencing as well as
70 whole-transcriptome sequencing. Moreover, gold standard diagnoses according to WHO
71 classification with all needed techniques, all performed in MLL, clinical data and therapy
72 response data are fully available for these cases. The main advantage of this reference

73 collection consists of the unambiguity of each diagnosis, providing a reference framework for
74 any further classification and diagnosis especially in difficult cases.

75 Therefore, SIRIUS will compare the diagnostic superiority of WGS or WTS to the combined
76 approach with gold standard results and by matching the obtained results to the nearest “digital
77 sibling” within our reference cohort of more than 5,500 WGS and WTS (both in 93% of cases).

78 To this end, we will use an inhouse developed matching algorithm, which is able to match
79 genomic or transcriptomic profiles to a group of similar cases and gold standard results from
80 timepoint of this study. Current workflows intended to generate WTS/WGS data from patient
81 samples – all while fulfilling state of the art accreditation (ISO 15189) – require up to 5 – 7
82 days. This is largely comparable to classical methods but holds the promise to replace error
83 prone and arduous iterations in the methodological work up. The objective is to test whether
84 WTS and/or WGS based approaches can surpass classical methods regarding diagnostic
85 precision and routine reliability. Here we will test this hypothesis in a prospective real-world
86 setting under diagnostically difficult circumstances.

87 **II. STUDY DESIGN**

88 1. Type of Study

89 SIRIUS is conducted as a monocentric prospective case-control study. The study population
90 consists of carefully chosen patients with potential hematological malignancy, for which
91 current diagnostic methods were not sufficient to provide clear-cut diagnosis and definitive
92 clinical guidance. SIRIUS is entirely a non-interventional study without therapeutic
93 consequences for direct patient care. Data will be used as research study and micro-cost
94 analysis will be provided.

95 2. Duration of Study

96 SIRIUS will be conducted for a total number of 110 patients with inconclusive diagnosis by
97 gold standard techniques for a total of up to nine months after the first enrollment. Patients to
98 qualify for study will be selected by referring center and PI before material is send to MLL.

99 3. Quality Control

100 Due to the heterogeneity in quality of blood and bone marrow samples arriving at MLL,
101 SIRIUS is preceded by a rigorous quality assessment of every patient history, data already
102 available and sample source and quality to be potentially included in the present study. The
103 minimal requirements are listed in III.

104 4. Primary Study Endpoints

105 Overall, the efficacy and supremacy of WGS/WTS analysis will be subjected to current
106 standard procedures. The primary endpoint will be assessed as follows: unclear cases will be
107 subjected to three diagnostic algorithms:

108 (1) Inhouse at referring site by histopathological diagnosis in the context of a hematological
109 tumor board according to current standards (“best practice”)

110 (2) Current gold-standard diagnostic workup as performed routinely by the MLL,
111 consisting of

112 a. Cytomorphological diagnosis
113 b. Immunophenotypic diagnosis
114 c. Chromosomal banding analysis
115 d. Molecular testing
116 e. NGS based Targeted panel sequencing

117 (3) WGS and WTS sequencing plus matching to nearest digital sibling in 5,5k cohort

118 The results of (2) and (3) arms will be first compared to the result obtained in (1) since this is
119 the therapy guiding approach *in domo*. Clinical follow-up observations will be made to assess
120 the success of this first diagnosis.

121 Next results from (2) and (3) will be compared against each other to obtain an assessment of
122 replaceability of current gold-standard methods to either WGS or WTS and WGS/WTS
123 combined. If both approaches do not yield a similar conclusion, specific data from (2) will be
124 added to results in (3) until a definitive assessment can be made.

125 5. Secondary Study Endpoints

126 • Turn-over time until potential therapy guiding diagnosis
127 • Cost-effectiveness until timepoint of diagnosis and therapy
128 • Compare WES to WGS data in SIRIUS cohort
129 • Identify number of potential actionable targets for which a therapy has been approved
130 but identification was missed in (1) and (2)
131 • Identify putative disease stage in comparison to (2) and clinical history

132

133

134 **III. SUBJECT SELECTION AND WITHDRAWAL**

135

136 1. Number Of Subjects

137 SIRIUS intends to enroll a total number of 110 cases provided by approximately 50 certified
138 hematological centers.

139

140 2. Gender, Age

141 Patients' samples from both sexes will be used (male and female). Only samples from adult
142 patients (18 years or older) will be used.

143

144 3. Inclusion Criteria

- 145 • Patients having been investigated with a suspected hematological disorder and:
 - 146 ○ Having unclear diagnosis after internal routine diagnosis
 - 147 ○ Unusual clinical course
 - 148 ○ Unusual r/r status or non-responder
 - 149 ○ Multiple parallel hematological conditions
 - 150 ○ Difficult/rare therapy associated/secondary neoplasms
- 151 • Current diagnostic work-up is not satisfactory in terms of (1) accuracy (2) clinical
152 behavior
- 153 • Only samples of patients min. 18 years of age will be used
- 154 • Material with a minimum of 20% tumor content in bone-marrow or peripheral blood
155 sample
- 156 • Samples must suffice quality attributes control which are denoted in (4.)
- 157 • Patient's informed consent

158 4. Exclusion Criteria

159 • Sample is not fit for state-of-the-art diagnosis, fails initial quality control. For quality
160 insurance we will exclude samples with wrong anticoagulant sent. Samples with
161 damage due to meteorological reasons (freeze-thaw damage or elevated temperature)
162 will be excluded.

163 • Samples with too scarce material jeopardizing routine gold-standard diagnosis will be
164 excluded (tumor content < 20 %).

165

166 5. Location

167 SIRIUS will be conducted as monocentric trial at the MLL.

168 **IV. STATISTICAL PLAN**

169

170 To determine the statistical significance within the endpoint analysis we will assess both
171 quantitative as well as qualitative variables. Quantitative variables will be described with the
172 number of non-missing values, mean, standard deviation, median, and minimum/maximum
173 values. Qualitative variables will be expressed as a number and percentage of patients with
174 each qualitative characteristic. The missing values are not intended to be included in the
175 calculation of percentages. Sensitivity and specificity will be assessed specific to each method,
176 with respect to internal gold standard diagnostic work-up.

177

178 **V. RISKS AND BENEFITS**

179 *Potential Direct Benefits to Subject*

180 Conducting SIRIUS will not bear any risks for patients enrolled in the study. Normal State-of-
181 the-art diagnosis is provided for each sample and prioritization of sample material in favor
182 current diagnostic material and reporting is performed to prevent jeopardization of gold
183 standard diagnosis.

184

185 **VI. DATA HANDLING AND RECORD**

186 Data management documents will be generated under the responsibility of the Sponsor. A
187 management plan will be issued before data collection begins and will describe all functions,
188 processes, and specifications for data collection, cleaning, and validation. The data
189 management documents will describe analysis methods and individuals who are authorized to
190 enter the data, decisions about ownership of data, source data storage, the origin and destination
191 of the data and who will always get access to the data. Data Management Responsibilities are

192 primarily handled by co-investigator [name]. Per request of external researchers,
193 the Sponsor will provide these investigators with additional data relating to the trial, duly
194 anonymized and protected in accordance with applicable requirements.

195

196 **VII. STUDY MONITORING, AUDITING, AND INSPECTION**

197 The Investigator will make all the trial-related source data and records available at any time to
198 quality assurance auditor(s) mandated by the Sponsor, or to domestic/foreign regulatory
199 inspectors or representatives who may audit/inspect the trial. The main purposes of an audit or
200 inspection are to assess compliance with the trial protocol and the principles of ICH-GCP
201 including the Declaration of Helsinki and all other relevant regulations.

202

203 **VIII. FINANCIAL CONSIDERATIONS**

204 The MLL is the main sponsor of this trial. Reagents for gold standard investigations will be
205 provided by MLL. Reagents for sequencing will be provided for by Illumina®, Inc. San Diego,
206 CA. All Data generated are fully owned by MLL. MLL will share aggregated and anonymized
207 data with Illumina®, i.e., without revealing patient sensitive data such as germline mutations.

208

209 **IX. CONFLICT OF INTEREST**

210 [name]. phil. Dr. med. [name] and [name]. med. [name] are part owners
211 of the MLL Munich Leukemia Laboratory.

212

213 **PUBLICATION PLAN**

214 The results obtained from SIRIUS will analyzed according to the guidelines of Good scientific
215 Practice of the German Science funding agency (DFG). Results that will be interesting for the

216 scientific community will be submitted and subsequently published in peer-reviewed academic
217 journals, according to the appropriate scope and audience.

218 At the end of the trial, one or more manuscripts for joint publication may be prepared in
219 collaboration between the Investigator(s) and financial sponsors. The PI reserves the right to
220 be last author(s) in all publications related to this trial. In the event of any disagreement in the
221 content of any publication, both the Investigator's and the Sponsor's opinion will be fairly and
222 sufficiently weighed and represented in the publication.

223

224 **X. ARCHIVING**

225 The PI is fully responsible for maintaining all the records (protocol and protocol amendments,
226 relevant correspondence, and all other supporting documentation), which enable the conduct
227 of the trial at the site to be fully understood, in compliance with ICH-GCP.

228 The study site should plan on retaining such documents for 10 years after study completion.
229 These documents should be retained for a longer period if required by the applicable regulatory
230 requirements or the hospital, institution, or private practice in which the study is being
231 conducted. Patient identification codes (patient names and corresponding study numbers) will
232 be retained for this same period.

233 **Trial Master File**

234 The Sponsor will archive the Trial Master File in accordance with ICH-GCP and applicable
235 regulatory requirements.

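### Section IV scores every method against the gold-standard work-up that is called inconclusive in these patients and that the study aims to surpass; the case-control label does not fit either

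*Protocol*

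**What the plan says.** - **Design (Protocol II.1).** "SIRIUS is conducted as a monocentric prospective case-control study". The population that follows is a single one: it "consists of carefully chosen patients with potential hematological malignancy, for which" current methods gave no clear answer.
- **Numbers (II.2, III.1).** "SIRIUS will be conducted for a total number of 110 patients with inconclusive diagnosis by" gold-standard techniques, and "SIRIUS intends to enroll a total number of 110 cases provided by approximately 50 certified" centers. No control group, control number or way of selecting controls is given.
- **Comparison (II.4).** Unclear cases are "subjected to three diagnostic algorithms": (1) the referring site's diagnosis, (2) the MLL gold-standard work-up, (3) WGS and WTS with matching to the reference collection. Algorithms (2) and (3) are each compared with (1), then with each other.
- **Eligibility (III.3, III.4).** "Material with a minimum of 20% tumor content in bone-marrow or peripheral blood" is an inclusion criterion. III.4 repeats it as an exclusion: "excluded (tumor content < 20" per cent.
- **Accuracy (IV).** "Sensitivity and specificity will be assessed specific to each method", taking the internal gold-standard work-up as reference. The target condition is not named.
- **Aim (I.2).** To test whether WGS and/or WTS can do better than classical methods in diagnostic precision and routine reliability.

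**The concern.** Sensitivity and specificity need a reference that is available for the patients analyzed and is more trustworthy than the tests being judged. Section IV uses as reference one of the three approaches under comparison. It is the approach that sequencing is meant to beat, and II.2 says its techniques were inconclusive in these patients. A plan followed as written could report lower accuracy for sequencing exactly where sequencing is right and the classical work-up is wrong.

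The design label adds to the confusion. A case-control diagnostic study would supply subjects without the condition, and hence a denominator for specificity. This study has none: it is one cohort with a within-patient comparison, and the tumor-content rule removes tumor-free subjects.

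**Working it through.** The protocol gives no expected sensitivity or specificity and no derivation of 110, so there is no figure to reproduce. The check takes the stated reference at its word and asks what it can deliver.

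**1. Design.** One group (II.1), 110 in total (II.2, III.1), three algorithms per patient (II.4). The collection of 5,500 samples in I.2 consists of hematological malignancies and serves for matching; it is not called a control group. The structure is a single-cohort paired comparison.

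**2. What the reference does to the comparison.** Suppose algorithm (2) resolves n of the 110 patients and assigns the wrong entity in e of them.
- The 110 − n unresolved patients have no reference class and drop out of both measures. These are the patients for whom sequencing was meant to help.
- Algorithm (2) against itself: n/n = 1.
- A perfect sequencing method against (2): (n − e)/n, which is at most 1.

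The same holds for each entity. If the reference has n_k patients with entity k, of whom e_k truly have another, a perfect test has apparent sensitivity (n_k − e_k)/n_k. If f_k of the n − n_k reference negatives truly have entity k, its apparent specificity is 1 − f_k/(n − n_k). Algorithm (2) scores 1 on both. So even with all 110 resolved, sequencing can at best tie.

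**3. Specificity, malignancy present versus absent.** Specificity = TN/(TN + FP). Eligibility requires at least 20% tumor content, so TN + FP = 0 of 110 and the ratio is 0/0.

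**4. Specificity, one entity versus the rest.** Patients with other entities are the negatives, so a denominator exists wherever algorithm (2) gives a class. The protocol states neither the resolved fraction nor the entity shares. The table assumes 110, 55 or 28 resolved, entity shares of 5%, 10% and 30%, and an observed specificity near 95%. Negatives = resolved − (resolved × share, rounded). Intervals are exact (Clopper-Pearson) 95%.

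| Resolved by (2) | Share | Negatives | Observed | 95% CI |
|---|---|---|---|---|
| 110 | 5% | 104 | 99/104 | 0.891–0.984 |
| 110 | 10% | 99 | 94/99 | 0.886–0.983 |
| 110 | 30% | 77 | 73/77 | 0.872–0.986 |
| 55 | 5% | 52 | 49/52 | 0.841–0.988 |
| 55 | 10% | 49 | 47/49 | 0.860–0.995 |
| 55 | 30% | 39 | 37/39 | 0.827–0.994 |
| 28 | 5% | 27 | 26/27 | 0.810–0.999 |
| 28 | 10% | 25 | 24/25 | 0.796–0.999 |
| 28 | 30% | 20 | 19/20 | 0.751–0.999 |
| 0 | any | 0 | none | not computable |

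Entity-level specificity is therefore computable without tumor-free controls. It describes only a subset selected for being resolvable, and it carries the distortion shown in step 2.

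**The case against.** A reader might infer that no specificity of any kind can be estimated, or that any reported value would be an artefact. The documents do not support that. The 0-of-110 count holds only if the target is malignancy present versus absent, and the protocol does not say so. The question in section I is classification among entities, for which step 4 finds negatives.

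Nor does the protocol establish that the MLL work-up fails in all 110. II.2 has patients selected before material reaches the MLL, and II.4 lists the MLL work-up separately from the referring site's diagnosis, so it may resolve some cases. Several entry routes in III.3, such as an unusual course or non-response, need not mean that a diagnosis is missing. The statement in II.2 that patients are inconclusive by gold-standard techniques sits badly with this reading, but that is a conflict of wording to reconcile. It does not prove that no reference result will exist.

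Two further defenses are fair in part. The target condition and the handling of indeterminate reference results are often left to an SAP, and no SAP is shown, so their absence is not held against the protocol. And no analysis in II.4 or IV uses case-control methods, so the label alone is a wording correction.

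What these points do not answer is the choice of reference, which the protocol itself fixes. Step 2 applies even if every patient is resolved. II.4 does provide for disagreements between (2) and (3), by adding data from (2) to (3) until an assessment is reached, but IV does not make that outcome the reference. An SAP could name a target condition; it could not supply patients whom eligibility excludes.

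**Conclusion.** The point holds in a limited form. The case-control label contradicts the described design. The accuracy rule in IV conflicts with the population in II.2 and with the aim in I.2: it gives no reference class for unresolved patients, a perfect score to algorithm (2) by construction, and an error for each correct sequencing result that differs.

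On size, malignancy-level specificity has no negatives among the 110. Entity-level specificity has between 0 and 104, depending on how many patients algorithm (2) resolves and on the entity's share. The resolved counts, entity shares and the value near 95% are assumptions. The argument in step 2 needs none of them. It rests on reading the internal gold standard in IV as algorithm (2), the most natural reading. The change should be made, though the study's data remain usable for a better-defined comparison.

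**What to change.** 1. **II.1:** replace the case-control label with prospective single-cohort paired diagnostic comparison.
2. **II.2 and IV:** reconcile the description of patients as inconclusive by gold-standard techniques with the use of the internal gold standard as reference. State whether the inconclusive work-up is the referring site's or the MLL's.
3. **IV, main comparison:** the proportion of the 110 with a definite diagnosis under each algorithm. If b patients are definite only under (2) and c only under (3), the paired difference is (c − b)/110, reported with a 95% CI. Fix in advance what counts as definite, because a nearest match in the collection can always be named. Use the planned clinical follow-up as supporting confirmation where available; II.4 plans it to judge the first diagnosis, so it will not confirm every algorithm.
4. **IV, comparison with (2):** report positive and negative agreement at entity level, restricted to cases that (2) resolves, with the number unresolved. Do not call it sensitivity or specificity.
5. **If specificity is wanted:** estimate it per entity by leave-one-out matching in the reference collection, whose diagnoses I.2 describes as unambiguous, and label it as applying to clear-cut cases. Both WGS and WTS exist for 93%, so about 0.93 × 5,500 = 5,115 samples could serve the combined method.

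The cost is a few changes of wording and a little more analysis on data already held or planned; no extra patients are needed. The downside is that no sensitivity or specificity figure will be available for the difficult cases themselves.

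### Entry selects on failure of gold-standard-type techniques, and the same class of techniques is then comparator (2), so the (2)-versus-(3) comparison probably leans towards WGS/WTS

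*Protocol*

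**What the plan says.** Five places in the protocol set who enters and what is compared.

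- **I.1** defines routine practice: the gold "standard of routine diagnostic process relies on five methodological pillars: cytomorphology", followed by histology, chromosomal cytogenetics, immunophenotyping and molecular genetics. It puts the share left unresolved at about 10%.
- **II.1** describes patients in whom "current diagnostic methods were not sufficient to provide clear-cut diagnosis and definitive" clinical guidance.
- **II.2** sets the number and the condition: "SIRIUS will be conducted for a total number of 110 patients with inconclusive diagnosis by" "gold standard techniques for a total of up to nine months after the first enrollment". The next sentence says that patients to "qualify for study will be selected by referring center and PI before material is send to MLL".
- **II.4** names three algorithms. (1) is the referring site's histopathological diagnosis with its tumour board. (2) is "Current gold-standard diagnostic workup as performed routinely by the MLL", with items a-e: cytomorphology, immunophenotyping, chromosome banding, molecular testing and a targeted NGS panel. (3) is WGS and WTS with matching to the reference cohort. After both are compared with (1), (2) and (3) are compared with each other to judge replaceability.
- **III.3** lists "Having unclear diagnosis after internal routine diagnosis" beside other features (unusual course, relapsed/refractory or non-responder status, parallel conditions, secondary neoplasms). It does not say whether each feature suffices alone.

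**The concern.** A head-to-head comparison of two diagnostic approaches is fair when entry does not depend more on the failure of one than of the other. Here entry depends on failure of the class of techniques that makes up (2), with no such condition on (3). Cases in which those techniques work well are removed before the comparison starts.

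I.2 asks whether WGS/WTS can surpass classical methods, and II.4 asks whether it can replace them. If part of the difference between (2) and (3) comes from who was let in, it cannot be read as a difference in diagnostic performance.

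The entry wording makes this harder to judge. II.2 speaks of gold-standard techniques and III.3 of an internal routine diagnosis. Neither says whose work-up, with which techniques, must have been inconclusive.

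**Working it through.** The protocol gives no resolution rates for (1), (2) or (3), so there is no stated figure to reproduce. The check is textual first. The numbers that follow illustrate direction and rough scale only.

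**1. Overlap.** Of the five pillars in I.1, four (cytomorphology, cytogenetics, immunophenotyping, molecular genetics) correspond to items a-d of (2). Histology is not in (2), and (2)e, the targeted panel, is listed in addition.

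**2. Timing.** Selection is by the referring centre and the PI, before material is sent. (2) is done at MLL. The inconclusive work-up is therefore a prior one, and (2) comes later.

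**3. When entry tilts the comparison.** Let q be the share of cases in which (2)'s techniques had been tried before entry, θ the yield of each method in the remaining cases (equal by assumption), r the chance that a repeat is again inconclusive, and s the yield of (3) in the previously tried cases.

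- Yield of (2) = q(1 − r) + (1 − q)θ
- Yield of (3) = qs + (1 − q)θ
- Gap = q[s − (1 − r)]

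Assume θ = 0.5 and r = 0.9. For q = 0.25, 0.5 and 1, (2) yields 0.40, 0.30 and 0.10.

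- If (3) is untouched by the earlier failure (s = 0.5), the gap is 0.4q: 10, 20 and 40 points.
- If s = 0.3, it is 0.2q: 5, 10 and 20 points.
- If s = 0.1, it is 0.

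The gap depends on q, which the protocol does not ask to be recorded, and on how far (3) fails in the same cases.

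**4. The same point with shared failures made explicit.** Let the entry work-up E, (2) and (3) each resolve p = 0.90 of unselected cases. For E and (2) this follows I.1's 10% unresolved; for (3) it is an assumption. Give each method a latent normal score with correlation ρ to E, and keep only cases that E failed. With t = Φ⁻¹(0.90) and Φ₂ the bivariate normal distribution function:

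P(resolve | E failed) = 1 − Φ₂(−t, −t; ρ)/(1 − p)

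| ρ with E | Resolved given E failed | Of 110 |
|---|---|---|
| 0 | 90.0% | 99.0 |
| 0.3 | 78.4% | 86.2 |
| 0.5 | 67.6% | 74.4 |
| 0.7 | 53.2% | 58.5 |
| 0.9 | 31.1% | 34.2 |
| 1 | 0% | 0 |

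Difference, (3) minus (2):

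- ρ = 0.7 for (2), 0.3 for (3): 78.4 − 53.2 = +25 points.
- ρ = 0.5 for (2), 0.3 for (3): 78.4 − 67.6 = +11 points.
- Equal ρ: 0.
- ρ = 0.3 for (2), 0.5 for (3): 67.6 − 78.4 = −11 points.

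All three methods are equally good by construction, so each difference comes from entry alone within the model. Its sign depends on which method shares more failures with E.

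**The case against.** A reader might infer that (2) merely repeats tests that have already failed in every patient, so that (3) must win through entry alone. The documents do not support that. Selection precedes receipt of material at MLL, so (2) is a new run in another laboratory, with a targeted panel listed, and it can still resolve cases. II.4 describes (1) as histopathological diagnosis, and no technique named there is on the (2) list. III.3 may admit patients for reasons other than a failed diagnosis. A tilt towards (3) is also not a logical necessity: it vanishes when shared failures are equal and can reverse.

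Three further objections have weight.

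- Difficult cases are chosen on purpose. I.2 says so, and asking how often WGS/WTS resolves unclear cases requires them. This stands for that added-yield question. It does not extend to a conclusion that (3) surpasses or replaces (2).
- Section IV assesses sensitivity and specificity against the internal gold-standard work-up. If that means (2), (3) cannot outscore (2) there. This stands, but it is a separate analysis and does not correct the head-to-head comparison.
- Splitting the analysis by prior work-up could be left to a statistical analysis plan. That is true of the analysis. The entry rule is fixed in the protocol, however, and an analysis plan can split by prior techniques only if they are recorded.

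**Conclusion.** The concern holds in a limited form. II.1 and II.2 select on prior failure of the class of techniques that forms comparator (2), nothing comparable applies to (3), and II.4 draws a replaceability conclusion from the comparison. A tilt towards (3) is likely because four of the five gold-standard pillars recur in (2), so (2) can be expected to share more failures with the earlier work-up than (3) does. That expectation is a judgement from the technique lists. The protocol does not state which techniques the referring sites used.

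The size is not determined. The figures of 11 and 25 points rest on assumed 90% yields and assumed correlations. The 10, 20 and 40 points rest on an assumed 50% yield, a 90% repeat-failure rate and no effect of entry on (3). None is an estimate of the bias in this study. The differing entry conditions in II.2 and III.3 are a plain textual fault, whatever the size.

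**What to change.** 1. Align II.2 with III.3, so that entry means inconclusive after the referring-site work-up (1), and use the same wording in II.1.
2. In the II.3 review of patient history and available data, record for each of techniques (2)a-e whether it had been done before entry, and where.
3. Report (2) versus (3) for all cases, and separately by whether those techniques had been used before.
4. Interpret previously worked-up cases as added yield after a failed gold-standard-type work-up, and confine any conclusion about surpassing or replacing gold-standard methods to pre-selected unclear cases.

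Step 1 alone does not remove the tilt if (1) already used overlapping techniques, so steps 2 to 4 are needed. Limiting the comparison to cases with no prior use of these techniques would go further but could leave few of the 110. Reporting both strata avoids that loss.

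The cost is wording, a few entry fields, and less precise subgroup estimates. For a yield near 50%, the 95% half-width is 1.96 × √(0.25/110) = 9.3 points in all cases and 1.96 × √(0.25/55) = 13.2 points in each half, if the split were even (an assumption).

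### The protocol does not fix the sequencing diagnosis (3) before (1) and (2) are known, and II.4 feeds (2) into (3) on disagreement, so agreement and accuracy may be biased upward

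*Protocol*

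**What the plan says.** - **Who does what.** II.4 lists route (2) as "2) Current gold-standard diagnostic workup as performed routinely by the MLL" and route (3) as "3) WGS and WTS sequencing plus matching to nearest digital sibling in 5,5k cohort". III.5 adds that "SIRIUS will be conducted as monocentric trial at the MLL", and I.2 says the matching algorithm was developed in-house. No sentence names who performs (3), but these statements together place it at the same laboratory.
- **What is known before inclusion.** II.3 says "SIRIUS is preceded by a rigorous quality assessment of every patient history, data already" available, along with sample source and quality. II.2 says that patients to "qualify for study will be selected by referring center and PI before material is send to MLL". The inclusion criteria in III.3 call for an unclear or otherwise problematic earlier picture.
- **Comparison.** II.4 first compares (2) and (3) with (1), and then: "Next results from (2) and (3) will be compared against each other to obtain an assessment of" whether current methods could be replaced by WGS, WTS or both.
- **Disagreement.** If (2) and (3) do not reach a similar conclusion, II.4 has selected data from (2) added to (3) until a definitive assessment is possible.
- **Accuracy.** Section IV measures sensitivity and specificity of each method against the internal gold-standard work-up, which is route (2).
- **Matching.** I.2 says the algorithm matches "genomic or transcriptomic profiles to a group of similar cases and gold standard results from" the time of the study.

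**The concern.** Whether sequencing could replace the routine work-up can only be judged from a sequencing diagnosis reached without the routine work-up. If the person who makes the (3) call can see (2), or if the (3) result is counted after data from (2) were added, part of the agreement is borrowed. The same applies to sensitivity and specificity, because (2) is also the reference standard.

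The exposure is greatest where judgement matters most, and the cohort is deliberately made up of difficult cases. Reading order and locking are also matters of laboratory conduct. If an unaided (3) call is never recorded, no later analysis can recover it, so this cannot be left to an analysis plan.

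**Working it through.** The protocol gives no figure that bears on this point. The 110 cases come without a target agreement, alpha, power or effect size, so there is nothing to reproduce. The check is a reading of the text, followed by an illustration.

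**Step 1: can (1) be known when (3) is read?** II.3 and II.2 show that the history and earlier data are examined before inclusion, with the PI taking part in selection. No sentence keeps that information from whoever makes the (3) call.

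**Step 2: can (2) be known when (3) is read?** The review in II.3 comes before the study's own (2), so it cannot disclose (2). The link to (2) comes from II.4. Both routes run in one laboratory, no reading order is stated, and data from (2) are openly added to (3) after a disagreement.

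**Step 3: which (3) result counts?** II.4 implies a first (3) conclusion, since otherwise no disagreement could be seen. It does not say that this conclusion is recorded and locked, nor that it, rather than the supplemented one, enters the comparison and the accuracy analysis. No rule is given for turning a match into a diagnosis.

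**Step 4: illustration with assumed values.** Let p be the agreement of (3) with (2) under independent reading, and f the share of discordant cases that move to agreement with (2) because (2) is known or added. Then

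observed agreement = p + f(1 − p).

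The protocol gives neither p nor f. The Wilson 95% interval at n = 110 shows sampling error for scale.

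| p (assumed) | Wilson 95% at n = 110 | f = 0 | f = 0.10 | f = 0.25 | f = 0.50 | f = 1 |
|---|---|---|---|---|---|---|
| 0.60 | 0.507 to 0.687 | 0.60 | 0.64 | 0.70 | 0.80 | 1.00 |
| 0.80 | 0.716 to 0.864 | 0.80 | 0.82 | 0.85 | 0.90 | 1.00 |

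In cases, for p = 0.60: 0.60 × 110 = 66 agree and 44 do not. With f = 0.25, 0.25 × 44 = 11 move, and (66 + 11)/110 = 0.70. With f = 0.50, 22 move, and 88/110 = 0.80.

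At f = 0.25 the shifted value lies just above the interval for p = 0.60 and inside it for p = 0.80. At f = 0.50 it lies clearly above both. At f = 1, which means every disagreement is settled in favour of (2), agreement is 100% whatever the truth.

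**The case against.** **Silence is not open reading.** A reader might infer that the laboratory is unmasked and that agreement is inflated. No sentence says so. Section VI promises a management plan before data collection, with documents on analysis methods and data access, and access rules may sit there. This stands: the bias is a risk, not an established result. It does not remove the step in II.4 that adds (2) to (3), which is explicit text.

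**II.3 carries less than it seems to.** A reader might infer that the laboratory's own readers review the history and thereby learn (2). The sentence names no reviewer, selection involves the referring center, and the review precedes the study's own (2). This stands. II.3 supports prior knowledge of (1) and the history at selection, and no more.

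**The matching phrase in I.2.** It could be read as making the patient's own (2) result an input. The more natural reading is that the profile is the input, and that the reference cases with their gold-standard diagnoses are what it is matched to. The reference to the time of the study leaves some ambiguity, which deserves a clarification only.

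**II.4 presupposes a prior (3) conclusion.** This is true, and it favours the sponsor. It still leaves open what the reader had seen by then and which (3) result is counted.

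**Direction and extent.** Borrowing from (2) would hide differences, and so would weaken a claim that sequencing surpasses classical methods. Some cases may also have no clear (2) diagnosis to borrow, and algorithmic matching may limit the effect. All of this is fair. The upward bias concerns agreement, replaceability, and sensitivity and specificity against (2).

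**History.** Withholding the history from readers of (3) but not of (2) would unbalance a real-world comparison. This stands, and the fix below takes it up.

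**Conclusion.** The point holds as a design weakness. A laboratory that follows the protocol as written can arrive at a (3) result that depends on (2), and nothing identifies the unaided (3) result as the one that counts. Agreement of (3) with (2), and sensitivity and specificity against the internal gold standard, may be biased upward.

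The documents do not allow the size to be determined. It ranges from nothing (f = 0) to complete agreement (f = 1), and the values between rest on assumed p and f. The conclusion also rests on the inference that (3) is done at the same laboratory as (2). It does not require that reading is in fact open.

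**What to change.** In II.4, state that:

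1. The WGS, WTS and combined calls of (3) are made from coded samples by existing staff without access to the results of (1) or (2), and are time-stamped and locked before those results are opened.
2. Route (2) is signed out without sight of (3).
3. Only the locked (3) calls enter the comparisons with (1) and (2) and the sensitivity and specificity analysis.
4. Any result obtained after data from (2) are added is reported separately as a supplemented result.
5. If clinical history is made available, readers of (2) and (3) receive the same history.

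In I.2, clarify that the gold-standard results used in matching are the reference cohort's diagnoses, not the study patient's own (2) result.

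The cost is a coding and lock step in the laboratory workflow. The sponsor's step of adding (2) to (3) is kept.
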